9.0 Confidentiality, Privacy and Data Management

9.1 Confidentiality

9.1.1 Identifiers associated with data and/or specimens See the Research Data Plan Review Form

9.1.1.1 Use of Codes, Master List

See the Research Data Plan Review Form

- 9.1.2 Storage of Data and/or Specimens See the Research Data Plan Review Form
- 9.1.3 Access to Data and/or Specimens See the Research Data Plan Review Form

9.1.4 Transferring Data and/or Specimens See the Research Data Plan Review Form

9.2 Subject Privacy

See the Research Data Plan Review Form

10.0 Data and Safety Monitoring Plan

10.1 Periodic evaluation of data

The PI and research study team will periodically evaluate the data and communicate regarding subject safety. Data collected for the first 20 patients will be summarized and submitted to the IRB for review to

ensure safety of subjects. This data will include information about image quality of the CTA examinations, any adverse events that occurred, and how many subjects required repeat scans.

- **10.2** Data that are reviewed Data acquired during low-contrast CTA will be reviewed.
- **10.3** Method of collection of safety information Data will be collected at time of screening and CTA
- **10.4** Frequency of data collection Data will be collected at time of screening and CTA
- **10.5** Individuals reviewing the data The PI and research study team will be responsible for reviewing data.
- **10.6** Frequency of review of cumulative data Cumulative data will be reviewed on a weekly basis by the principal investigator and study team members.
- **10.7** Statistical tests Statistical tests are as outlined in section 8.2 and 8.3.
- **10.8** Suspension of research Not Applicable

11.0 Risks

There is a minimal risk of loss of confidentiality.

There is a risk of increased radiation if the scan needs to be repeated due to a non-diagnostic clinical exam. If the exam is non-diagnostic due to inadequate vascular enhancement, the examination will be repeated. This may lead to an increased radiation dose to the patient. It is important to note that non-diagnostic studies can, and do occur with the standard volume of contrast currently administered for these examinations. When this occurs, the examination is repeated with a second standard or reduced dose of contrast. Given the low dosage of intravenous contrast of the planned low dose protocol, a repeat examination can be performed without exceeding the standard of care contrast dose to the patient,

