2.0 Background

2.1 Scientific Background and Gaps

Currently, at our institution, routine CTA examinations are obtained with a dose of 100mL of intravenous contrast. In the setting of renal dysfunction, this dose is reduced to 75mL to minimize the risk of contrast induced nephropathy. This dose can be further adjusted giving some flexibility depending on the BMI of the patient and type of scanner used. Given the recent advancements of computed tomography hardware, the scanning speed has greatly increased allowing for reduction in contrast dose. However, at our institution, the dosage and administration rate of intravenous contrast has not yet been adjusted to take advantage of improvements in scanning hardware.

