7.2 Study Procedures

7.2.1 Clinic Visit

The process of obtaining the CTA images will be unchanged from the patient's standpoint. One difference will be that the examination will be supervised by a team member. The intravenous contrast dose administered will be decreased according to the parameters written above. If the study is deemed non-diagnostic at the time of scanning, the study will be repeated. The standard of care at this institution in the setting of a non-diagnostic study is to repeat the study with a 75mL dose of contrast, for a total of 175mL of contrast. Given that the dose of contrast that will be administered for this study (40-50mL) is below the routine amount (100mL). Performing a repeat study with 75mL of intravenous contrast will not exceed the contrast dose that would have been normally administered.

7.2.2 EXAMPLE: Visit 2 or Day 2 or Post-test, etc. (format accordingly) Not Applicable

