7.4 Test Article(s) (Study Drug(s) and/or Study Device(s))

7.4.1 Description

Intravenous contrast, Omnipaque, will be administered as described above. The intravenous contrast is FDA approved for use of CTAs and is a standard of care practice at PSHMC with the standard contrast dose of 100 mL.

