7.4.2 Treatment Regimen

At this institution, CTAs are performed with the standard contrast dose of 100 mL. This study will administer intravenous contrast, Omnipaque, at a dosage of 40 mL at a rate of 5mL/sec or at 50 mL at a rate of 5mL/sec as described above.

- 7.4.3 Method for Assigning Subject to Treatment Groups Not Applicable
- 7.4.4 Subject Compliance Monitoring Not Applicable
- 7.4.5 Blinding of the Test Article Not Applicable

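### Do sections 7.2.1 and 11.0 wrongly assure that a repeat scan stays within the standard contrast dose?

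*Combined protocol and SAP*

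**What the plan says.** All references are to the combined protocol and SAP.

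- **Study dose (7.1).** 40 mL for CTA of the chest, and 50 mL for the other listed regions.
- **Single-scan standard dose.** Section 7.4.1 says Omnipaque "is a standard of care practice at PSHMC with the standard contrast dose of 100 mL". Section 7.4.2 says that at this institution "CTAs are performed with the standard contrast dose of 100 mL".
- **Repeat scan (7.2.1).** A non-diagnostic study scan is repeated. The institution's practice after a non-diagnostic scan is to "repeat the study with a 75mL dose of contrast, for a total of 175mL of contrast". The section then mentions the routine 100 mL and concludes: "Performing a repeat study with 75mL of intravenous contrast will not exceed the contrast dose that would have been normally administered".
- **Risks (11.0).** The section observes that non-diagnostic scans also happen at the standard volume. Of those it says: "When this occurs, the examination is repeated with a second standard or reduced dose of contrast". It then states that, because the study dose is low, "a repeat examination can be performed without exceeding the standard of care contrast dose to the patient".
- **Background (2.1).** The other place with a 75 mL figure: "In the setting of renal dysfunction, this dose is reduced to 75mL".
- **Safeguards.** Section 3.2 excludes GFR below 60 and says this is so that a repeat can be done without added renal risk. Section 7.1 records dose with the scan details. Section 10.1 sends the IRB a summary of the first 20 patients that includes "any adverse events that occurred, and how many subjects required repeat scans".

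**The concern.** Two things look wrong.

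First, neither assurance says what it is measured against. Someone who looks up the standard dose in 7.4.1 or 7.4.2 finds 100 mL. A study scan plus a 75 mL repeat is more than that, so on this reading both assurances are false. The subject who matters is one whose low-dose scan fails although a single 100 mL scan would have sufficed: the trial has then given that person more contrast, not less.

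Second, 7.2.1 gives one repeat dose (75 mL), while 11.0 speaks of a standard or a reduced dose, which on the documents' own figures could be 100 mL or 75 mL. If both described the same study subject, the repeat dose would be uncertain by 100 − 75 = 25 mL.

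At stake would be how accurately the plan describes contrast exposure for subjects who are repeated.

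**Working it through.** **Inputs.** Study dose 40 or 50 mL (7.1); repeat dose 75 mL and repeated-routine total 175 mL (7.2.1); single standard dose 100 mL (7.4.1, 7.4.2).

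**Step 1: reproduce the plan's figure.** Routine scan plus repeat = 100 + 75 = 175 mL, as stated in 7.2.1.

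**Step 2: total for a repeated study subject.** Total = study dose + repeat dose.

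| Region | Total | Against 175 mL (routine scan, repeated) | Against 100 mL (single routine scan) |
|---|---|---|---|
| Chest | 40 + 75 = 115 mL | 115 − 175 = −60 mL | 115 − 100 = +15 mL |
| Other regions | 50 + 75 = 125 mL | 125 − 175 = −50 mL | 125 − 100 = +25 mL |

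The assurances are true against 175 mL and false against 100 mL, so everything depends on which is meant.

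**Step 3: which comparator the text supports.** In 7.2.1 the subject is what happens after a non-diagnostic scan. The 175 mL total is given for exactly that event, and the conclusion follows shortly after. In 11.0 the assurance comes directly after the remark that standard-volume scans are sometimes non-diagnostic and are then repeated. In both places the comparison is one repeated course with another. The 100 mL in 7.2.1 serves a different purpose: it explains why the study course starts from a lower base.

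**Step 4: whether the repeat doses conflict.** The sentence in 11.0 about a standard or reduced dose refers back to non-diagnostic scans at the standard volume, so it describes routine practice. A reduced dose includes 75 mL, so it is compatible with 7.2.1. The only repeat figure applied to a study scan is the 75 mL in 7.2.1. The 25 mL gap appears only if the sentence in 11.0 is moved to a group it does not describe.

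**Step 5: robustness.** Suppose, against that reading, a repeat of 100 mL. The totals would be 40 + 100 = 140 mL and 50 + 100 = 150 mL. These remain below 175 mL, and below the 100 + 100 = 200 mL of two standard doses. The documents contain none of these three totals. The assurance against a repeated routine scan therefore does not depend on how the sentence in 11.0 is read.

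**Step 6: statistical consequences.** Section 8.2 rests on a 7.5% equivalence margin, 80% power and a 5% level; section 8.3 uses paired t-tests. Neither uses the repeat dose or its comparator.

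**The case for a change.** The best case for a change is that a risk statement should not need interpretation. In 7.2.1 the figure nearest the conclusion is 100 mL, not 175 mL. Section 7.4.1 links standard of care with 100 mL in one sentence, and 11.0 then uses a very similar phrase with no figure. Section 2.2 says repeats are rare, so what a patient would normally receive can fairly be taken as one scan. The 175 mL comparison suits a subject whose routine scan would also have failed; it does not suit one for whom 100 mL would have been enough. Section 11.0 names extra radiation from a repeat but not extra contrast, and the 10.1 summary counts repeats without giving contrast volumes.

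Some of this stands. The comparator is unnamed, and a reader could be misled by 15 or 25 mL for a subject who is repeated. The rest carries less weight:

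- Section 11.0 breaks off at a comma and the consent pages are not available, so what subjects are told about contrast cannot be judged from this text.
- The total contrast for a repeated subject can be worked out from the doses recorded under 7.1, provided the repeat injection is entered with the first. Listing it in the 10.1 summary would be a preference, and leaving it out contradicts nothing.
- The renal question for a repeated scan was foreseen: the GFR exclusion in 3.2 was written for it, repeats and adverse events in the first 20 patients go to the IRB, and section 10.6 has cumulative data reviewed weekly.
- The documents give no repeat rate, so the number of subjects concerned cannot be derived. It is at most the number of repeats, because those who would also have failed at 100 mL receive less contrast than the repeated routine course.

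**Conclusion.** The concern does not call for a change. The sums are right: a repeated study subject totals 115 or 125 mL, which is 60 or 50 mL below the repeated routine course and 15 or 25 mL above a single routine scan. Read in context, both assurances compare with the repeated course and are true. The defect is an unnamed comparator, not a wrong figure, and the two descriptions of the repeat dose do not contradict each other.

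Naming the comparator would be tidier drafting, but it would alter nothing that is done, measured or analysed.

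This rests on two assumptions: that 175 mL is the intended comparator, which the order of the text in 7.2.1 and 11.0 supports but does not state; and that the 75 mL in 7.2.1 is the repeat dose for study subjects, since no other figure is given for them. No view is taken on which dose or repeat rule is appropriate.

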12.0 Potential Benefits to Subjects and Others

12.1 Potential Benefits to Subjects

There is no guaranteed benefit from participating in this study. Potential benefits to the patient include a decrease in contrast dose which inevitably reduces the risk for development of contrast induced nephropathy.

12.2 Potential Benefits to Others

Given the increasing number of contrast enhanced studies performed in the hospital each day, the risk of contrast induced nephropathy has theoretically increased. Specific populations of patients are susceptible to contrast induced nephropathy. Avoidance of this complication by low dose examinations can preserve renal function and potentially decrease hospital stay and health care costs.

13.0 Sharing Results with Subjects

Not Applicable

14.0 Subject Stipend (Compensation) and/or Travel Reimbursements

Not Applicable

15.0 Economic Burden to Subjects

15.1 Costs

Subjects will not be responsible for any cost for participating in the study other than their standard of care imaging. The repeat CTA scan, contrast and administration, if required, will be provided at no cost to patient.

15.2 Compensation for research-related injury

It is the policy of the institution to provide neither financial compensation nor free medical treatment for research-related injury. In the event of injury resulting from this research, medical treatment is available but will be provided at the usual charge. Costs for the treatment of the research-related injuries will be charged to subjects or their insurance carriers.

16.0 Resources Available

16.1 Facilities and locations

The research will be conducted in the department of Radiology at Penn State Hershey Medical Center [name].

16.2 Feasibility of recruiting the required number of subjects

Study investigators regularly see patients for CTA scans. Therefore, the ability to recruit 180 subjects is feasible.

16.3 PI Time devoted to conducting the research The PI has devoted time to academic endeavors.

16.4 Availability of medical or psychological resources Hershey Medical Center's Emergency Department is available 24/7.

16.5 Process for informing Study Team

Ultra-low dose protocols will be presented to the Radiation Awareness Group (RAG) committee in the Radiology department. Following approval, the CT technologists will be made aware of the protocol changes in selected patients meeting inclusion criteria. In addition, the PI or team members will be available to oversee the examination.

17.0 Other Approvals

17.1 Other Approvals from External Entities Not Applicable

17.2 Internal PSU Committee Approvals

Check all that apply:

Anatomic Pathology – Hershey only – Research involves the collection of tissues or use of pathologic specimens. Upload a copy of the Use of Human Tissue For Research Form on the "Supporting Documents" page in CATS IRB. This form is available on the IRB website at: http://www.pennstatehershey.org/web/irb/home/resources/forms

Animal Care and Use – All campuses – Human research involves animals and humans or the use of human tissues in animals
Biosafety – All campuses – Research involves biohazardous materials (human biological specimens in a PSU research lab, biological toxins, carcinogens, infectious agents, recombinant viruses or DNA or gene therapy).
Conflict of Interest Review – All campuses – Research has one or more of study team members indicated as having a financial interest.
Radiation Safety – Hershey only – Research involves research-related radiation procedures. All research involving radiation procedures (standard of care and/or research-related) must upload the Radiation Review Form on the "Supporting Documents" page in CATS IRB. This form is available on the IRB website at: http://www.pennstatehershey.org/web/irb/home/resources/forms
IND/IDE Audit – All campuses – Research in which the PSU researcher holds the IND or IDE or intends to hold the IND or IDE.
Scientific Review – Hershey only – All investigator-written research studies requiring review by the convened IRB must provide documentation of scientific review with the IRB submission. The scientific review requirement may be fulfilled by one of the following: (1) external peer-review process; (2) department/institute scientific review committee; or (3) scientific review by the Clinical Research Center Advisory committee. NOTE: Review by the Penn State Hershey Cancer Institute Scientific Review Committee is required if the study involves cancer prevention studies or cancer

patients, records and/or tissues. For more information about this requirement see the IRB website

at: http://www.pennstatehershey.org/web/irb/home/resources/investigator

18.0 Multi-Site Research

- **18.1** Communication Plans Not Applicable
- **18.2 Data Submission and Security Plan** Not Applicable
- **18.3 Subject Enrollment** Not Applicable
- **18.4** Reporting of Adverse Events and New Information Not Applicable
- 18.5 Audit and Monitoring Plans Not Applicable

19.0 Adverse Event Reporting

19.1 Reporting Adverse Reactions and Unanticipated Problems to the Responsible IRB In accordance with applicable policies of The Pennsylvania State University Institutional Review Board (IRB), the investigator will report, to the IRB, any observed or reported harm (adverse event) experienced by a subject or other individual, which in the opinion of the investigator is determined to be (1) unexpected; and (2) probably related to the research procedures. Harms (adverse events) will be submitted to the IRB in accordance with the IRB policies and procedures.

20.0 Study Monitoring, Auditing and Inspecting

20.1 Auditing and Inspecting

The investigator will permit study-related monitoring, audits, and inspections by the Penn State quality assurance program office(s), IRB, the sponsor, and government regulatory bodies, of all study related documents (e.g., source documents, regulatory documents, data collection instruments, study data etc.). The investigator will ensure the capability for inspections of applicable study-related facilities (e.g., pharmacy, diagnostic laboratory, etc.).

21.0 Future Undetermined Research: Data and Specimen Banking

- 21.1 Data and/or specimens being stored Not Applicable
- 21.2 Location of storage Not Applicable
- 21.3 Duration of storage Not Applicable
- 21.4 Access to data and/or specimens Not Applicable
- 21.5 Procedures to release data or specimens Not Applicable
- 21.6 Process for returning results Not Applicable

